APPENDIX 8: COMMON TERMINOLOGY CRITERIA FOR GRADING OF ADVERSE EVENTS (25)

Grading of toxicity and adverse events will be made according to the Common Terminology Criteria for Adverse Events (CTCAE) version 4. The full CTCAE document is available in the Investigator Site File and on the National Cancer Institute (NCI) website. The following address was correct when this version of the protocol was approved:

http://ctep.cancer.gov/protocolDevelopment/electronic_applications/ctc.htm

APPENDIX 9: EuroQoL EQ-5D-5L QUALITY OF LIFE QUESTIONNAIRE

Health Questionnaire

English version for the UK

Under each heading, please tick the ONE box that best describes your health TODAY. **MOBILITY**

I have no problems in walking about	
I have slight problems in walking about	
I have moderate problems in walking about	
I have severe problems in walking about	
I am unable to walk about	
SELF-CARE	
I have no problems washing or dressing myself	
I have slight problems washing or dressing myself	
I have moderate problems washing or dressing myself	
I have severe problems washing or dressing myself	
I am unable to wash or dress myself	
USUAL ACTIVITIES (e.g. work, study, housework, family or leisure activities)	
I have no problems doing my usual activities	
I have slight problems doing my usual activities	
I have moderate problems doing my usual activities	
I have severe problems doing my usual activities	
I am unable to do my usual activities	
PAIN / DISCOMFORT	
I have no pain or discomfort	
I have slight pain or discomfort	
I have moderate pain or discomfort	
I have severe pain or discomfort	
I have extreme pain or discomfort	_
ANXIETY / DEPRESSION	
I am not anxious or depressed	
I am slightly anxious or depressed	
I am moderately anxious or depressed	
I am severely anxious or depressed	
I am extremely anxious or depressed	

The best health you can imagine

The worst health you can imagine

- We would like to know how good or bad your health is TODAY.
- This scale is numbered from 0 to 100.
- 100 means the best health you can imagine.
 0 means the worst health you can imagine.
- Mark an X on the scale to indicate how your health is TODAY.
- Now, please write the number you marked on the scale in the box below.

YOUR HEALTH TODAY =

APPENDIX 10: MPN-SAF QUALITY OF LIFE QUESTIONNAIRE

Myeloproliferative Neoplasm Symptom Assessment Form (MPN-SAF)

Instructions: Please fill out all questions, as best able, reflecting how these symptoms affected you over the **LAST WEEK** unless directed otherwise. Complete forms until the STOP instruction toward the end of the packet.

Symptom	1 to 10 (0 if absent) ranking* 1 is most favorable and 10 least favorable			
Please rate your fatigue (weariness, tiredness) by circling the one number that best describes your fatigue right NOW	(No Fatigue) 0 1 2 3 4 5 6 7 8 9 10 (Worst Imaginable)			
Please rate your fatigue (weariness, tiredness) by circling the one number that best describes your USUAL level of fatigue during past 24 hours	(No Fatigue) 0 1 2 3 4 5 6 7 8 9 10 (Worst Imaginable)			
Please rate your fatigue (weariness, tiredness) by circling the one number that best describes your WORST level of fatigue during past 24 hours	(No Fatigue) 0 1 2 3 4 5 6 7 8 9 10 (Worst Imaginable)			
Circle the one number that describes how, during the past 24 hours, fatigue has interfered with your				
General activity	(Does not Interfere) 0 1 2 3 4 5 6 7 8 9 10 (Completely Interferes)			
• Mood	(Does not Interfere) 0 1 2 3 4 5 6 7 8 9 10 (Completely Interferes)			
Walking ability	(Does not Interfere) 0 1 2 3 4 5 6 7 8 9 10 (Completely Interferes)			
Normal work (includes work both outside the home and daily chores)	(Does not Interfere) 0 1 2 3 4 5 6 7 8 9 10 (Completely Interferes)			
Relations with other people	(Does not Interfere) 0 1 2 3 4 5 6 7 8 9 10 (Completely Interferes)			
Enjoyment of life	(Does not Interfere) 0 1 2 3 4 5 6 7 8 9 10 (Completely Interferes)			

Circle the one number that describes how, during the past Week how much difficulty you have had with each of the following symptoms			
(Absent) 0 1 2 3 4 5 6 7 8 9 10 (Worst Imaginable)			
(Absent) 0 1 2 3 4 5 6 7 8 9 10 (Worst Imaginable)			
(Absent) 0 1 2 3 4 5 6 7 8 9 10 (Worst Imaginable)			
(Absent) 0 1 2 3 4 5 6 7 8 9 10 (Worst Imaginable)			
(Absent) 0 1 2 3 4 5 6 7 8 9 10 (Worst Imaginable)			
(Absent) 0 1 2 3 4 5 6 7 8 9 10 (Worst Imaginable)			
(Absent) 0 1 2 3 4 5 6 7 8 9 10 (Worst Imaginable)			
(Absent) 0 1 2 3 4 5 6 7 8 9 10 (Worst Imaginable)			
(Absent) 0 1 2 3 4 5 6 7 8 9 10 (Worst Imaginable)			
(Absent) 0 1 2 3 4 5 6 7 8 9 10 (Worst Imaginable)			
(Absent) 0 1 2 3 4 5 6 7 8 9 10 (Worst Imaginable)			
(Absent) 0 1 2 3 4 5 6 7 8 9 10 (Worst Imaginable)			
(Absent) 0 1 2 3 4 5 6 7 8 9 10 (Worst Imaginable)			
(Absent) 0 1 2 3 4 5 6 7 8 9 10 (Worst Imaginable)			
(Absent) 0 1 2 3 4 5 6 7 8 9 10 (Worst Imaginable)			
(Absent) 0 1 2 3 4 5 6 7 8 9 10 (Daily)			
(Absent) 0 1 2 3 4 5 6 7 8 9 10 (Worst Imaginable)			
(As good as it can be) 0 1 2 3 4 5 6 7 8 9 10 (As bad as it can be)			

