8 SCHEDULE OF STUDY ASSESSMENTS

	Screening		Сус	cle 1	Сус	cle 2	Cycle 3 Cycle 4		le 4	Cycle 5		Cycle 6		;	Treatment can be	Loss of	
Week		1	1	3	5	7	9	11	13	15	17	19	21	23	25	continued as long as	response /
Day	Day -28 to 0	1	2	15	29	43	57	71	85	99	113	127	141	155	169	response is maintained - maximum follow-up interval 4 weeks	Disease progression / Intolerability
Informed consent	✓																-
Screening - eligibility criteria	✓																
Medical and CMML history	✓																
Demographic data	✓																
Concomitant medications	✓	✓			✓		✓		✓		✓		✓		✓	✓	✓
Transfusion history	✓	✓			✓		✓		✓		✓		✓		✓	✓	✓
Physical Examination	✓	✓			✓		✓		✓		✓		✓		✓	✓	✓
Vital Signs, Weight	✓	✓			✓		✓		✓		✓		✓		✓	✓	✓
Performance score (ECOG)	✓														✓		✓
Haematology	✓	✓		1	1	✓	✓	✓	✓	✓	✓	✓	✓	1	✓	✓	✓
Biochemistry	✓	✓		✓	✓	✓	✓	✓	✓	✓	✓	✓	✓	✓	✓	✓	✓
Coagulation screen	✓																
Urinalysis	✓	✓		✓	✓		✓		✓		✓		✓		✓		✓
Blood and bone marrow for central correlative studies	✓								✓						✓		
Pregnancy test (1)	✓	✓			✓		✓		✓		✓		✓		✓	✓	
ECG	✓	✓			✓		✓		✓		✓		✓			✓	
Bone marrow assessment (2)	✓								✓						✓		✓
QoL questionnaires	✓								✓						✓		
Dispensation of study medication		✓			✓		✓		✓		✓		✓		✓	✓	
Blood samples for acetylation studies (3)		✓	✓	✓	✓												
Blood samples for pharmacokinetic studies (4)		✓	✓	✓	✓												
Adverse event assessment		Monitor during treatment and for 30 days after last dose of tefinostat															
Progression / AML transformation	Monitor from day of registration to end of trial																

⁽¹⁾ Pregnancy test (urine) should be performed within 1 week of each study cycle in women of childbearing potential

⁽²⁾ Bone marrow examination should be performed at baseline, after 3 and 6 cycles of treatment and, for patients continuing beyond 6 cycles of tefinostat, at the time of stopping drug due to loss of response / disease progression or toxicity. At each of these time-points blood and bone marrow samples will be shipped for central biological correlative studies

⁽³⁾ Blood for acetylation studies will be taken pre-dose on day 1, 1hrs, 2hrs and 4hrs post dose on day 1, pre-dose on day 2, pre-dose on day 15 and pre-dose on day 29 (day 1 of cycle 2)

⁽⁴⁾ Blood for pharmacokinetic studies will be taken pre-dose on day 1, 1 hrs, 2hrs and 4hrs post dose on day 1 and pre-dose on day 2, pre-dose on day 15 and pre-dose on day 29 (day 1 of cycle 2)

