8.1 Baseline assessments (day -28 to 0)

The following screening and baseline assessments should be performed within the period of 28 days prior to commencing the first cycle of tefinostat therapy (days -28 to 0). Some of these assessments may have been conducted as routine clinical practice prior to the patient's entry into the trial.

The following will be recorded / obtained for all patients:

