8.1.8 Samples for central assessment and biological studies

- Separate samples of blood and bone marrow should be obtained at the time of the baseline assessment for correlative biological and biomarker studies including determination of molecular genetic profile, protein acetylation profile and hCE-1 expression level
- 4ml bone marrow and 20ml peripheral blood should be placed in EDTA tubes clearly labelled with trial number, patient initials and date of birth
- Investigators will be supplied with a collection kit which should be sent to the reference laboratory at the address below using the enhanced Royal Mail delivery service and the account reference number provide with the collection kit:

[name] Department of Haematology School of Medicine **Cardiff University** [name]

[name]

[contact]

Email: [contact]

It is also intended to store excess patient material for future research. It is mandatory to obtain the patient's specific consent to do so. For this purpose Patient Information Sheet 2 and Consent Form 2 should be used. Copies of Consent

Form 2 should be stored in the study file on site, in the patient's notes and a copy given to the patient. If a patient has

not consented to storage of excess material, the local site team should inform the CTR staff who will arrange to have

any remaining material destroyed.

8.1.9 **Quality of life assessments**

Patients should complete the EuroQol EQ5D-5L and MPN-SAF questionnaires (see Appendix 9 and 10). Completed

questionnaires should be returned to CTR using the pre-paid envelopes provided, or by scan and email.

Treatment assessments during tefinostat cycles 1-6 8.2

Each patient will receive a minimum of six 28-day cycles of tefinostat treatment, subject to tolerability. Cycles will run

continuously. During cycles 1-6 (weeks 1-24), patients will be assessed fortnightly - on day 1 and on day 15 (+/- 2 days) of each

cycle. The following will be assessed:

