8.2.1 Clinical assessment (each cycle)

Adverse events (day 1 and 15)

Concomitant medications (day 1 only)

Transfusion history – at day 1 of cycle 1 this should include any transfusions administered between screening and the

start of cycle 1, for other cycles it should include any transfusions over the preceding 28 days.

Physical examination including liver and spleen size by palpation, lymph nodes, skin infiltration, gingival

hypertrophy(day 1 only)

Vital signs and weight (day 1 only)

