- Neutrophils If pre-treatment neutrophils $\leq 0.5 \times 10^9/I$: increase to $> 0.5 \times 10^9/I$ (and by $\geq 100\%$)
 - If pre-treatment neutrophils 0.5-1.0 x 10^9 /I: an absolute increase of \geq 0.5 x 10^9 /I (and by at least 50%)
- **Spleen** either a minimum 50% reduction in palpable splenomegaly of a spleen that is a least 10cm palpable at baseline or a spleen that is palpable at more than 5cm at baseline becoming not palpable
- **Symptoms** improvement in symptoms as noted by a decrease of ≥50% in the MPN-SAF Total Symptom Score (only valid if baseline score>20)*

Disease Progression (requires a combination of either 2 major, 1 major & 2 minor, or 3 minor criteria from the list below)

Major Criteria of disease progression

Increase in bone marrow blast count: -<5% blasts: ≥50% increase (and to >5% blasts)

- 5-10% blasts: ≥50% increase (and to >10% blasts)

- 10-20% blasts: ≥50% increase (and to >20% blasts)

Evidence of cytogenetic evolution: - appearance of new cytogenetic abnormality

- increase in cytogenetic burden of disease by ≥50%

• New extramedullary disease: - worsening splenomegaly (either from previously inpalpable to

>5cm palpable, or >100% increase in previous 5-10cm

splenomegaly, or ≥50% increase in previous >10cm splenomegaly)

- extramedullary disease outside the spleen (including hepatomegaly, skin lesions, granulocytic sarcoma)

Minor Criteria of disease progression

- New transfusion dependence (at least 2u of red cells in the past month for Hb<85g/l that was not associated with clinically overt bleeding or felt to be associated with therapy
- Significant loss of maximal response of cytopenias: ≥50% decrement from maximum response in neutrophils or platelets (not felt to be associated with therapy)
- Reduction in Hb by 15g/l from best response or baseline (not felt to be associated with therapy)
- Increase in symptoms as noted by an increase of ≥50% in the MPN-SAF Total Symptom Score*
- Evidence of molecular clonal evolution

^{*} The use of the MPN-SAF Total Symptom Score within the International Consortium MDS/MPN Response Criteria is currently considered exploratory. Validation among patients within MDS/MPN is currently under way. (28)

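### The only pre-treatment MPN-SAF may be up to 28 days old at the first dose and is not repeated on day 1, so symptom change before treatment, in either direction, can be counted as change on tefinostat in the primary response.

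*Protocol*

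**What the plan says.** **Recall period.** Appendix 10 tells patients to answer "reflecting how these symptoms affected you over the LAST WEEK unless directed otherwise". Some fatigue items are shorter: one asks about the present moment, and another for the number that "best describes your USUAL level of fatigue during past 24 hours".

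**When baseline is taken.** Protocol 8.1 says of the screening and baseline assessments that they "should be performed within the period of 28 days prior to commencing the first cycle of tefinostat therapy". The questionnaires are one of these assessments (8.1.9): "Patients should complete the EuroQol EQ5D-5L and MPN-SAF questionnaires (see Appendix 9 and 10). Completed" forms go back to the trials office. Section 9.2 also describes a single reading before treatment, then readings after cycles 3 and 6.

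**Schedule table (section 8).** The row "QoL questionnaires" is ticked at screening, day 85 and day 169, and not on day 1. Haematology, physical examination and transfusion history are ticked on day 1.

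**Use in the endpoint.** Appendix 3 lists as one Clinical Benefit item "improvement in symptoms as noted by a decrease of ≥50% in the MPN-SAF Total Symptom Score (only valid if baseline score>20"). One item is enough if there is no CR, PR or progression. The requirement for two analyses over at least eight weeks is written for blood counts only. Section 10.4.1 makes Clinical Benefit or better the primary efficacy outcome, and 10.1 applies it at 3 of 19 and 7 of 40 patients.

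**The concern.** A form with a one-week recall, completed on day -28, describes a week that ended four weeks before the first dose. Nothing in the protocol narrows the window for the questionnaires. The protocol itself expects events in that interval: on transfusion history at cycle 1 day 1, section 8.2.1 says "this should include any transfusions administered between screening and the" start of cycle 1. Eligible CMML-1 patients include those with transfusion dependence or symptomatic anaemia (5.1), and some patients enter on hydroxycarbamide (7.5). Their symptoms may well differ between screening and day 1.

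The screening score then does four jobs: it is the denominator of the 50% fall, it decides whether the symptom item is open to the patient at all (baseline above 20), it is the natural reference for symptom progression, and it is the starting point for quality-of-life change. A pre-dose shift can misclassify a patient on any of these. An analysis plan cannot repair this later, because a day 1 form that was never collected cannot be recovered.

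**Working it through.** **1. The gap.** The baseline may precede dose 1 by up to 28 days. With a 7-day recall, up to about 3 to 4 weeks before treatment may be covered by no form.

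**2. How a shift changes the classification.** Take three invented scores, 40, 26 and 20.
- Improvement before dosing: screening 40, day 1 26, week 24 20. From screening, (40 − 20)/40 = 50%: responder. From day 1, (26 − 20)/26 = 23%: not.
- Worsening before dosing: screening 26, day 1 40, week 24 20. From screening, 23%: not a responder. From day 1, 50%: responder.
- Threshold: screening 26, day 1 20. The symptom item is open on the first value and closed on the second.

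The error runs both ways.

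**3. The plan's own design figures.** Inputs from 10.1: 19 patients then 21 more, at least 3 responses in stage 1, at least 7 of 40 in all, response rates 10% and 30%. The probability of passing both efficacy gates at true rate p is

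P(p) = Σ (x = 3 to 19) Pr[Bin(19, p) = x] × Pr[Bin(21, p) ≥ 7 − x].

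At p = 0.10:

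| Stage 1 responses | Pr | Pr of enough in stage 2 | Product |
|---|---|---|---|
| 3 | 0.1796 | 0.1520 | 0.0273 |
| 4 | 0.0798 | 0.3516 | 0.0281 |
| 5 | 0.0266 | 0.6353 | 0.0169 |
| 6 | 0.0069 | 0.8906 | 0.0061 |
| 7 or more | 0.0017 | 1 | 0.0017 |

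The sum is 0.080, within the stated 10%. At p = 0.30 it is 0.941. The toxicity rule passes with probability 0.911 at 20% toxicity, so joint power, taking response and toxicity as independent, is 0.941 × 0.911 = 0.857, against the stated 85%. The design reproduces.

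**4. Sensitivity of the gates.** The same formula gives 0.117 at p = 0.11 and 0.162 at p = 0.12. One percentage point of spurious response takes the efficacy error above 10%.

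**5. Does pre-dose change produce spurious response?** The documents give no rate of pre-dose symptom change, so this can only be illustrated. Assumptions: no drug effect; scores with mean 30 and SD 15, kept within 0 to 100; correlations 0.8 (screening and day 1), 0.6 (day 1 and week 24) and 0.55 (screening and week 24); where there is a shift, 30% of patients move by about a quarter before dosing. False symptom response:

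| Scenario | Screening baseline | Day 1 baseline |
|---|---|---|
| Improvement, persisting to week 24 | 11.0% | 6.7% |
| Improvement, gone by week 24 | 8.3% | not needed here |
| Worsening, persisting to week 24 | 7.3% | 7.5% |
| No pre-dose change | 8.3% | 7.3% |
| No pre-dose change, both week-24 correlations 0.60 | 7.3% | 7.3% |

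Improvement that fades leaves the screening-baseline rate at its no-change level of 8.3%. Persistent worsening reverses the sign. The 8.3% against 7.3% with no pre-dose change comes only from assuming 0.55 rather than 0.60.

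**The case against.** The passages agree with each other, so this is a design choice and not a contradiction. Day -28 is a permitted limit, and a site that has the form completed just before dosing complies. Both points stand and bear on severity.

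A reader might infer that symptoms are the only response component with an old baseline. The documents do not support that. Re-measuring counts, spleen and transfusions on day 1 does not make day 1 their baseline, and the bone marrow, which drives remission and marrow response, also has only a screening value before treatment.

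A reader might also infer that the response rate is inflated and the error rate doubled or more. That is not shown. Section 10.4.1 reads response at day 29 of the sixth or last cycle, so an earlier change counts only if it still shows then. Section 7.5 does not permit hydroxycarbamide after cycle 3, and 5.2 excludes uncontrolled ongoing infection, which limits two of the obvious causes. Entrants include symptomatic patients who need treatment, so worsening before dose 1 is at least as plausible as improvement. Null rates such as 11% or 12% are chosen to show sensitivity; adding a symptom excess to overall response would ignore overlap with other response items and the no-progression condition.

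Finally, the protocol never lists the items in the Total Symptom Score, so the 24-hour fatigue item is not shown to enter it. The last-week recall carries the argument without it.

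The reply that the score is labelled exploratory (9.2, Appendix 3) does not remove the point: nothing takes the score out of the primary endpoint, and 8.3.6 says it is part of the criteria.

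**Conclusion.** The point holds in a limited form. The only pre-treatment symptom score can be up to four weeks old at the first dose, and one later form is enough for a primary response. Change before dosing, in either direction, can therefore misclassify symptom response, access to the symptom item, symptom progression and quality-of-life change. How often this would happen, and which way it would tip the response rate, cannot be derived from the protocol. What can be derived is that the efficacy rule has little slack: 0.080 at a 10% response rate, 0.117 at 11%, 0.162 at 12%. These are exact binomial results and do not estimate the effect of this problem. Low severity, worth correcting because it is cheap and cannot be corrected afterwards.

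**What to change.** In 8.1.9, 8.2 and the schedule table, have the MPN-SAF and EQ-5D-5L completed on cycle 1 day 1 before the first dose. Define that value as baseline for symptom response (including the above-20 condition), symptom progression and quality of life. Use the screening form only if the day 1 form is missing.

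The cost is one extra or moved questionnaire session per patient, at a visit that already takes place. The change removes only the pre-dose part of symptom fluctuation. It leaves untouched the reliance on a single unconfirmed reading and the absence of a control arm.

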APPENDIX 11: SUMMARY OF NON-CLINICAL INFORMATION GUIDANCE FOR THE INVESTIGATOR

Tefinostat (CHR-2845) is an investigational compound in development for cancer.

Chemical and Physicochemical Description

CHR-2845 and CHR-2845.tartrate are white to pale yellow solids. CHR-2845 has low solubility in water (< 0.01 mg/mL), but is more soluble at pH 2.0 (10 mg/mL). Dry-fill, size 0, hard gelatin capsules containing 10, 40 and 80 mg CHR-2845 and 120 mg CHR-2845.tartrate are available.

Pharmacology

CHR-2845 is an HDACi with pleiotropic activity against a range of human cancer cells in vitro. It exerts profound anti-proliferative effects against monocytic tumour cell lines. As a consequence of the species specific cleavage of tefinostat by the monocyte-specific carboxylesterase and its instability in rodent plasma, evaluation of CHR-2845 in rodent models would not reflect its potential benefit in human disease.

Pharmacokinetics

The plasma concentration of CHR-2845 and its acid, CHR-2847, has been determined in PK studies. Bioavailability in the dog (47 %) is higher than in the monkey (6-13 %). Bioavailability in the monkey following administration of CHR-2845.tartrate is 9 % (equivalent to that with tefinostat freebase when administered as a suspension (10 %). CHR-2845 is rapidly converted to its acid metabolite, CHR-2847, in rodent plasma. The elimination half-life of CHR-2845 is 0.66 hours and 0.21 hours in the monkey and dog, respectively, and for CHR-2847 it is 1.23 and 1.1 hours for the monkey and dog, respectively. Following 28-day repeat dosing in the rat, CHR-2847 levels increased with dose (although not dose proportionally) and total exposure (AUC0-t) was approximately 50 % greater in females than males. Exposure to CHR-2847 doubled at the highest dose level (300 mg/kg/day) on Day 28 when compared to the Day 1 (lower doses were unaffected). Following 28-day repeat dosing in the monkey, CHR-2845 and CHR-2847 levels increased with dose (sub-dose proportionally in males and supra-dose proportionally in females), with total exposure (AUC0-t) 3-fold and 4-fold greater in the females for CHR-2845 and CHR-2847, respectively.

The data show that there is a sex difference in the TK parameters with greater exposure in females when dosed orally with CHR-2845 in monkeys. This pattern has not been observed in humans, although only a small number of patients have been evaluated to date.

Tefinostat is a moderate inhibitor (IC50 2.67 μ M) of CYP3A4 with nifedipine as a substrate. Tefinostat inhibition of CYP3A4 was less potent when using testosterone and midazolam as substrates with IC50 values of 41.1 and 75.3 μ M, respectively. Tefinostat did not inhibit the activity of any of the other CYP450 isoforms tested (IC50 > 100 μ M). CHR-2847 is a weak inhibitor of CYP3A4 with nifedipine as a substrate, with an IC50 of 55.6 μ M. CHR-2847 did not inhibit the activity of any of the other CYP450 isoforms tested (IC50 > 100 μ M).

Based on these data, it is considered possible that tefinostat may participate in, or contribute to, drugdrug interactions which are mediated by CYP3A4.

Incubation of tefinostat with male CD-1 mouse, Sprague-Dawley rat, beagle dog, cynomolgus monkey and human hepatocytes resulted in measurable metabolism of tefinostat in all species. The rank order rate of metabolism of tefinostat was dog > rat > human > mouse > monkey. An examination of metabolic profiles by LC-MS/MS indicated that there is a similar pattern of metabolites in hepatocytes from all species investigated.

Toxicology

Toxicological data which are adequate to support early phase clinical studies have been generated. The available data comprise an evaluation of the potential to exert adverse pharmacological effects on the cardiovascular, respiratory and nervous systems, together with oral toxicity studies of 28 days duration in the rat and monkey, and evaluation of the potential to induce mutations in bacteria and chromosomal aberrations in cultured CHO cells.

There was no drug-related effect on hERG channel activity in transfected CHO cells. There were no adverse effects on a functional observational battery or motor activity in male albino rats given a single oral dose of up to 300 mg/kg. Single oral doses of up to 450 mg/kg were without effect on cardiovascular and respiratory parameters in conscious monkeys.

The acute median lethal oral dose for male and female rats is > 2000 mg/kg. During a 28-day oral toxicity study in the rat, animals treated at 300 mg/kg/day were noted to have salivation and fur/coat staining in the peri-oral area. Reduced body weight gain associated with reduced food intake was noted for males treated at 100 and 300 mg/kg/day. An increase in spleen weight at the end of the 28-day treatment period for animals dosed at 300 mg/kg/day. The study identified a potential to induce a reversible mild regenerative anaemia at 300 mg/kg/day. The no observable adverse effect level (NOAEL) for this study was considered to be 100 mg/kg/day.

During a 28-day oral toxicity study in monkeys, males treated at 450 mg/kg/day showed dehydration, whilst both males and females at this dose level showed a slight reduction in body weight, with recovery evident during the 28-day recovery period. As in the rat, there was evidence of a reversible, regenerative anaemia in all treated groups. Platelet count was increased for males at females treated at 150 and 450 mg/kg/day and activated partial thromboplastin times were longer for animals treated at 450 mg/kg/day. There was recovery from these changes following cessation of dosing. A decrease in lymphocytes in animals dosed at 450 mg/kg/day was noted at the end of the treatment period.

Although this was not statistically significant, it was still evident at the end of the 28-day recovery period. Clinical chemistry changes noted included increased total bilirubin (all dose levels), increased urea (females, all dose levels) increased asparatate aminotransferase, alanine aminotransferase and lactate dehydrogenase (450 mg/kg/day), decreased cholesterol (150 and 450 mg/kg/day) and increased creatinine (150 and 450 mg/kg/day). Decreased thymus weight was apparent at the end of the treatment period for all dose levels and was still evident at the end of the 28-day recovery period for females. Moderate or marked thymic atrophy was noted at 450 mg/kg/day with mild atrophy evident for individual animals dosed at 50 and 150 mg/kg/day. This finding was still evident in females at a reduced severity on completion of the 28-day recovery period. Accumulation of haemosiderin (mild or moderate) in Kupffer cells was present in the liver of animals treated at 450 mg/kg/day and females at 150 mg/kg/day with minimal accumulation observed sporadically in the remaining treatment groups. The finding was still evident in females at a reduced severity on completion of the 28-day recovery period. Minimal or mild centrilobular hepatocyte hypertrophy or minimal or mild hepatocyte degeneration was evident for individual animals at 150 and 450 mg/kg/day. These findings were not evident at the end of the 28-day recovery period. Mild periportal fatty vacuolation was observed at the end of the 28-day recovery period in one animal of each sex previously dosed at 450 mg/kg/day. A NOAEL could not be defined for this study.

Tefinostat appears to be devoid of mutagenic potential in bacteria and whilst it has been shown to induce a higher than control incidence of chromosomal aberrations in cultured CHO cells, this is only apparent at concentrations of 200 and 210 μ g/mL (in the presence of S9 mix) which are toxic to the test cells.

The data suggest that subjects entered into clinical studies should be carefully monitored for evidence of haematological toxicity.	

